#### **IV. RESEARCH DESIGN AND METHODS**

##### **Overview**

Given that majority of participants screened will not be eligible, we plan to screen 5000 individuals with the expectation that 10% will be eligible. We propose to recruit 500 eligible

patients from the ongoing MoodNetwork and the Health eHeart Alliance studies who self-report a history of depression and are at elevated risk for cardiovascular events. 40% of participants (2000) will be recruited from MoodNetwork, while 60% (3000) will be recruited from Health-eHeart. Participation will take a total of 16 weeks. During the first 8 weeks, participants will receive online CBT and a fitbit device to track activity, online MBCT and a fitbit device to track activity, or a fitbit device to track activity but no adjunctive therapy. The second 8 weeks are a follow-up period where participants will be asked to continue wearing their fitbit device, but receive no other form of treatment, regardless of which group they were initially randomized to. Participants will use desktop computers, laptops, tablet devices, or phones to participate in this study. These procedures are described in detail below.

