Accessed through a links managed by MoodNetwork.org and Health-eHeart.org, interested participants will sign an online consent form waiver, found in a web portal hosted by the Eureka mHealth Research Platform. Eureka is a multi-tenant system (architecture in which a single instance of a software application serves multiple customers), which is housed on a HIPAA compliant Amazon cloud database. Once the participant has read and electronically signed the waiver of consent form, participants will register for Eureka and then complete a short battery of assessments to determine eligibility. The assessments will consist of 3 standard psychological assessments (The Patient Health Questionnaire [PHQ-9], the Altman Self-Rating Mania Scale [ASRM], and the Mini International Neuropsychiatric Interview [MINI], and 2 cardiac health assessments (The Duke Activity Status Index [DASI], and the International Physical Activity Questionnaire [IPAQ]). They will also be asked to complete a standard demographic form, and their medical and psychiatric histories. If they are not eligible, they will be thanked for their interest and informed that unfortunately, they are not eligible. If found eligible, they will provide their mailing address information so that we can ship them a Fitbit device. Once they receive their Fitbit device, they will return to the study portal to sync their fitbit with our system so that we can collect their step data complete a series of questionnaires, including the World Health Organization Composite International Diagnostic Interview for Bipolar Spectrum Disorders (CIDI), The Patient Health Questionnaire (PHQ-9), The Altman Self-Rating Mania Scale (ASRM), The Sheehan Disability Scale (SDS), The World Health Organization-5 Well-Being Index (WHO-5), the Self Efficacy for Exercise (SEE), the International Physical Activity Questionnaire (IPAQ), the Seattle Angina Questionnaire-7 (SAQ-7) and the Perceived Stress Scale (PSS). Once completed, participants will be randomized to CBT + Fitbit, MBCT + Fitbit, or the Fitbit-only control group. Those who are randomized to one of the two therapy-based treatment groups will be sent to a portal on MoodNetwork.org to access the interventions. Those randomized to the Fitbit-only treatment group will be brought to a page thanking them for their participation, reminding them to wear their fitbit for the next 16 weeks, and informing them that they will be emailed reminders when they need to return to the portal to complete surveys. All participants, regardless of study group, will be asked to return to Eureka in weeks 2, 4, 6, 8, and 16 to complete a battery of assessments and asked questions about adverse events that may have occurred since beginning the study (detailed in Table 1 below).

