**The Perceived Stress Scale (PSS)** is the most widely used psychological instrument for assessing perception of stress. This scale measures the extent to which situations in one's life are labeled as stressful.

**Self Efficacy for Exercise (SEE)** is a 13-item instrument that focuses on self-efficacy expectations related to the ability to continue exercising in the face of barriers to exercise.

**International Physical Activity Questionnaire (IPAQ)** The IPAQ was developed to assess cross-national monitoring of physical activity and inactivity. It is validated in 12 countries and is available in both a long and a short form.

**Cardiac Events (CE)** is a two - question survey designed to monitor participants who may develop contraindications to exercise or who are at elevated risk for a cardiac event over the course of the study.

**Seattle Angina Questionnaire – 7 (SAQ-7)** is a well-validated and widely used 19-item instrument that measures patient-reported symptoms, function and quality of life for patients with coronary artery disease.

**Adverse Event Questions (AEQ)** two-question survey designed to assess if participant has experienced any adverse events, related to the study, since starting to participate.

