**a. Safety and Monitoring**

The PI ([name]) and the study staff will discuss participant safety in person or via conference call on a regular basis. They will discuss and resolve any safety issues, as such issues arise - for example, the occurrence of adverse events, possible participant withdrawal from the study, or a score of full depression, hypomania/mania or suicidal ideation. [name] will be responsible for preparing a written report that summarizes these discussions and any decisions that are made pertaining to participant disposition. He will also be responsible for determining whether the research should be altered or stopped.

In addition, there will be a Data Safety and Monitoring Board (DSMB) for this study composed of (1) three Massachusetts General Hospital clinical researchers experienced in conducting randomized clinical trials for depression (2) an expert in assessing and treating cardiovascular disease; (3) an expert in biostatistics; and (4) a patient stakeholder with cardiovascular disease. This DSMB will monitor safety issues, including the review of adverse events, the PI's quarterly report of the study's progress, all IRB amendments, and the adequacy and integrity of accumulating data. The purpose of this process is to assess scientific integrity and patient safety issues, and ensure the ethical conduct of the trials. The DSMB will approve the initiation of the study and subject enrollment, and determine if study procedures should be altered or stopped due to evidence of benefit or harm to trial subjects that may be attributable to the study or reasons related to scientific integrity. The PI will submit quarterly reports to the DSMB detailing any study changes, adverse events, subject recruitment and retention, reasons for early termination, and ongoing data reports. The PI will also respond to all DSMB issues and queries.

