**b. Adverse Events**

Researchers will follow all ethical and professional reporting requirements for adverse events. Reporting of adverse events will occur as follows (procedures below are consistent with requirements of the Partners IRB):

1) Serious adverse events that are reportable according to the guidelines of the Office for Human

Research Protections (OHRP) and FDA (e.g., death, suicide attempt, inpatient hospitalization) will be reported by telephone within 2 business days to the IRB of MGH.

A full written report of the event will be sent to the MGH IRB within 1 week of the event's occurrence.

2) Any other unanticipated problems occurring will be reported to the IRB within 2 weeks, in accordance with guidelines of the Office for Human Research Protections (OHRP) and FDA.

3) All adverse events will be summarized in the PCORI and IRB annual progress reports.

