### C. Rate of Attrition

Some attrition (i.e., 20%) is expected and this can result in bias and reduce power, precision and generalizability. Consistent with the Intent to Treat principle, we will continue with the assessments for the study duration, even among those who fail to comply with the treatment.

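### The adverse event survey is asked five times with a cumulative recall window, and the plan describes no onset date, linkage of repeats or counting unit

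*Combined protocol and SAP*

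**What the plan says.** The Overview in section IV (Research Design and Methods) says that all participants "will be asked to return to Eureka in weeks 2, 4, 6, 8, and 16 to complete a battery of assessments", and that at those visits they are "asked questions about adverse events that may have occurred since beginning the study". Section IV.c (Diagnostic and Clinical Assessments) describes the Adverse Event Questions as a two-question survey "designed to assess if participant has experienced any adverse events, related to the study, since starting to participate". Table 1 marks the survey at the same five visits. Two separate places therefore give a window running from study start to the day of the survey, so this is not a slip in one sentence.

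On use of the data, section VII.b says "All adverse events will be summarized in the PCORI and IRB annual progress reports", and section VII.a says "This DSMB will monitor safety issues, including the review of adverse events", supported by quarterly reports from the principal investigator. Section VIII (Data Analysis) contains no adverse event analysis. Nowhere do the documents mention an onset date, a rule for linking a repeat report to an earlier one, or whether summaries count events or people.

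A side issue: the Overview asks about adverse events generally, while section IV.c limits the survey to events related to the study. Those two descriptions need reconciling, but the present point concerns only the recall window.

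**The concern.** Each survey's window contains all the earlier ones. A participant who had an event in week 1 and answers as asked will truthfully answer yes at all five visits. Two things can then go wrong.

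- **Repeats.** If positive answers are added across visits without linkage, early events are counted several times and late events once. Participation lasts 16 weeks, which is longer than a quarter (52/4 = 13 weeks), so one event could also appear in successive quarterly reports.
- **Masking.** Once someone has answered yes, a genuinely new event produces the same answer at the next visit. Nothing described in the plan separates the two.

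What is at stake is the clarity of the safety summaries that go to the funder, the IRB and the DSMB. Whether repeats can be identified depends on what is asked at the time. An onset date that was not collected at the survey is hard to recover later, so a rule written at the analysis stage may come too late.

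**Working it through.** The plan gives no adverse event count or rate, so there is no stated figure to reproduce. The check counts how many recall windows contain an event, according to when it began.

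**Inputs from the documents**
- Survey weeks: 2, 4, 6, 8, 16 (section IV Overview; Table 1).
- Window: study start to the current survey (section IV Overview; section IV.c).
- Length: "Participation will take a total of 16 weeks" (section IV Overview).
- Attrition, for sensitivity only: "Some attrition (i.e., 20%) is expected" (section VIII.C).

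**Assumptions, not in the documents**
- Study start is week 0.
- Onset is evenly spread over weeks 0-16.
- The probability of repeating an already reported event at each later survey is r, from 0 to 1.
- In the attrition run, dropout is linear over the 16 weeks.

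**Step 1. Windows containing an event, by onset**

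| Onset (weeks) | Windows |
|---|---|
| 0-2 | 5 |
| 2-4 | 4 |
| 4-6 | 3 |
| 6-8 | 2 |
| 8-16 | 1 |

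**Step 2. Mean reports per event, all surveys completed, r = 1**

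(2×5 + 2×4 + 2×3 + 2×2 + 8×1)/16 = 36/16 = 2.25.

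For events in the 8 treatment weeks only: (2×5 + 2×4 + 2×3 + 2×2)/8 = 28/8 = 3.5.

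**Step 3. Partial re-reporting**

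The mean number of later windows is (2×4 + 2×3 + 2×2 + 2×1 + 8×0)/16 = 20/16 = 1.25, so mean reports per event = 1 + 1.25r.

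| r | Mean reports per event |
|---|---|
| 1 | 2.25 |
| 0.75 | 1.94 |
| 0.5 | 1.63 |
| 0.25 | 1.31 |
| 0 | 1.00 |

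**Step 4. 20% attrition, r = 1**

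The proportion still present at week w is 1 − 0.2w/16. Expected reports are proportional to the sum of w(1 − 0.2w/16) over the five visits: 1.95 + 3.80 + 5.55 + 7.20 + 12.80 = 31.3. Events are proportional to the integral of the same function over 0-16, which is 16 − 1.6 = 14.4. The ratio is 31.3/14.4 = 2.17, so attrition of this size hardly changes the result.

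**Step 5. Alternatives**

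With interval windows (0-2, 2-4, 4-6, 6-8, 8-16) each event falls in exactly one window. Linking repeats by onset date also gives one record per event. Participants with at least one event is a per-person count, so repeats do not inflate it under either window.

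**The case against.** The strongest reply is that no error has been shown. A reader might infer that the trial's event counts are wrong. The documents do not support that: they give no count and no rule that survey answers will be summed, and the standard summary of participants with at least one event is immune to repeats. This stands.

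A reader might also infer that the survey cannot separate a new event from an old one. The two items are not reproduced, and one of them might ask for a description or a date. What can be said is that the documents do not describe how repeats are distinguished.

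Nor do the documents say that the annual summaries and the DSMB review rest on this survey alone. Section VII.a has the investigator and staff discussing events as they arise. Section VII.b requires individual reporting of serious events. Section VI adds alerts from the depression and mania scales and a separate cardiac survey. Handling at case level may reveal some repeats, and the coded identifiers in section VI (Ensuring Confidentiality) make linkage within a participant feasible.

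A cumulative window also has a merit: someone who skips a survey or forgets to mention an event gets another chance. This stands and affects the choice of fix.

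What the reply does not remove is the stated recall rule. Feasible linkage still needs something to link on, and no onset date is mentioned. Counting participants with at least one event avoids inflation but says nothing about second events.

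**Conclusion.** The point holds as a weakness in how safety data are collected, and it should be corrected. As described, a later positive answer from someone who has already answered yes may be a repeat or a new event. Five reports of one event is the maximum and applies only to onset in the first two weeks; events after week 8, half of the 16-week period, fall in one window. The means of 2.25 overall and 3.5 for the treatment phase are upper bounds, resting on evenly spread onset, full completion, full re-reporting and unlinked summing. The lower bound is 1.0.

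A reader might go further and infer a biased comparison of harm between arms. The documents do not support that. All arms share one survey schedule and no between-arm adverse event test is planned. A spurious difference would need unlinked summing together with an arm difference in survey completion, re-reporting or event timing, and none of these is documented. The primary and secondary efficacy outcomes are not affected.

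**What to change.** Choose one of two versions, and make the same change in the section IV Overview and in section IV.c.

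1. **Interval version.** Ask about new events since the last completed survey, with an onset date for each. Anchoring on the last completed survey, rather than the last scheduled one, keeps events from a missed visit. The first survey should still run from the beginning of the study, not from randomisation, because participants receive and sync the Fitbit before they are randomised and events in that period should be kept.
2. **Cumulative version.** Keep the present question, add an onset date for each event, and link repeats by participant and onset date.

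Under either version, state in section VII.b or section VIII that summaries will give unique events and participants with at least one event, by arm.

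The cost is one extra item for those who answer yes and a sentence on counting; the interval version also needs new question wording. The interval version loses the second chance to report an event left out of a completed survey. The cumulative version keeps it, but relies on dates being recalled consistently enough to match.

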### **Participant Selection and Recruitment**

Participants (N = 5000) will be recruited from MoodNetwork.org and health-ehartstudy.org. Participation will take 16 weeks and will involve (1) 8 weeks of receiving online CBT and use of a fitbit, MBCT and use of a fitbit, or use of a fitbit with no adjunctive therapy and (2) 8 weeks of follow-up. Participants will use desktop computers, laptops, tablet devices, or phones to participate in this study. An IRB approved electronic alteration of a written Informed Consent will be obtained from all patients before protocol-specified procedures are carried out. Patients will be recruited according to the following criteria:

#### **a. Inclusion Criteria**

- Ability to give informed consent
- Fluent in English
- Between the ages of 18-65
- Lives in the United States
- Self-report of having experienced depression as assessed by the Mini International Neuropsychiatric Interview (MINI)
- Self report an elevated risk for or of having cardiovascular disease ( < 150 minutes of physical activity a week)
- Registered a personal account with Fitbit prior to enrollment in the study

#### **b. Exclusion Criteria**

- Unwilling/unable to comply with study procedures
- Pregnant

- Responds to item 9 (Suicidal ideation) on the PHQ-9 with a 3 (i.e., “Thoughts that you would be better off dead or of hurting yourself in some way nearly every day”)
- Contraindications to exercise or diet interventions as assessed by the DASI
- Already uses a fitbit device or other activity monitor
- Suffers from repeated episodes of “blacking out” or “fainting”
- Survived a cardiac arrest
- Has recurrent chest discomfort with activity that goes away within 10 minutes of rest or with nitroglycerin
- Has heart failure
- Has been hospitalized recently (within past 6 weeks) for a cardiovascular problem

### c. Diagnostic and Clinical Assessments

#### **Diagnostic and Clinical Assessments:**

**The Mini International Neuropsychiatric Interview (MINI)** The MINI can assess for current 17 Axis I diagnoses, exploring lifetime diagnoses where clinically relevant (i.e., previous manic episode for a diagnosis of bipolar disorder). Diagnoses can be ruled out by answering no to one or two screening questions. Positive responses to screening questions are followed by further exploration of other diagnostic criteria. The MINI shows good specificity and sensitivity for most psychiatric diagnoses and concordance with other structured diagnostic interviews.

**The World Health Organization Composite International Diagnostic Interview for Bipolar Spectrum Disorders (CIDI)** is a 12-item fully-structured lay-administered diagnostic interview that was validated as being capable of generating conservative diagnoses of both threshold and sub-threshold bipolar disorder.

**The Duke Activity Status Index (DASI)** is a 12-item self-administered questionnaire that utilizes self-reported physical work capacity to estimate peak metabolic equivalents and has been shown to be a valid measurement of functional capacity.

**The Patient Health Questionnaire-9 (PHQ-9)** is a brief self-report instrument used to screen, diagnose, monitor, and measure the severity of depression. The first 8 questions incorporate DSM-IV diagnostic criteria as well as other major depressive symptoms, and Question 9 assesses for the presence and duration of suicidal ideation.

**The Altman Self-Rating Mania Scale (ASRM)** is a brief (5-item) self-report questionnaire that helps measure the severity or intensity of manic or hypomanic symptoms.

**The Sheehan Disability Scale (SDS)** measures functional impairment resulting from depressive, panic, anxiety, or phobic symptoms. Patients rate the extent to which their work/school work, social life/leisure activities, and family responsibilities/home life are affected on a 10-point scale. Patients also indicate the number of days lost and number of days underproductive due to symptoms.

**The World Health Organization-5 Well-Being Index (WHO-5)** is a brief self-report (5-item) of positively-worded statements related to positive mood (good spirits, relaxation), vitality (being active and waking up fresh and rested), and general interests (being interested in things) over the prior two weeks.

**The Perceived Stress Scale (PSS)** is the most widely used psychological instrument for assessing perception of stress. This scale measures the extent to which situations in one's life are labeled as stressful.

**Self Efficacy for Exercise (SEE)** is a 13-item instrument that focuses on self-efficacy expectations related to the ability to continue exercising in the face of barriers to exercise.

**International Physical Activity Questionnaire (IPAQ)** The IPAQ was developed to assess cross-national monitoring of physical activity and inactivity. It is validated in 12 countries and is available in both a long and a short form.

**Cardiac Events (CE)** is a two - question survey designed to monitor participants who may develop contraindications to exercise or who are at elevated risk for a cardiac event over the course of the study.

**Seattle Angina Questionnaire – 7 (SAQ-7)** is a well-validated and widely used 19-item instrument that measures patient-reported symptoms, function and quality of life for patients with coronary artery disease.

**Adverse Event Questions (AEQ)** two-question survey designed to assess if participant has experienced any adverse events, related to the study, since starting to participate.

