3. Patients will complete the brief, bi-weekly survey of potential cardiovascular symptoms (CE) to monitor participants throughout the study. The survey will ask patients whether they have been hospitalized for any of a variety of cardiac conditions. Patients who respond affirmatively to any of the components of the CE (specifically any of the choices 1-7 in question 1) will be automatically prompted to stop engaging in any excessive physical activity (including activity related to study) and to seek medical attention from their primary provider before proceeding. Study staff will be alerted in these situations and may follow-up directly with the participant.
4. Subjects may be withdrawn from the study for any of the following: 1; 1) Elevated risk for a cardiac event as confirmed by Cardiac Events assessment 2) Clinically significant or serious adverse event not consistent with continuation in study, as determined by subject or study clinicians; 3) Subject's decision to withdraw. Any subjects that are withdrawn from the study will be asked to contact their treating physician for any follow up care.

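### One section limits the adverse event survey to study-related events, which conflicts with two other sections; a survey built that way may miss events

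*Combined protocol and SAP*

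**What the plan says.** Three sections bear on what the survey covers.

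- Section IV.c, entry for the Adverse Event Questions (AEQ): a "two-question survey designed to assess if participant has experienced any adverse events, related to the study, since starting to participate".
- Section IV, Overview: participants in every group "will be asked to return to Eureka in weeks 2, 4, 6, 8, and 16 to complete a battery of assessments" and are "asked questions about adverse events that may have occurred since beginning the study". No limit on cause is given. The AEQ row of Table 1 shows the same five weeks.
- Section VII.b: "All adverse events will be summarized in the PCORI and IRB annual progress reports". The same section gives examples of serious events by outcome, not by cause: "e.g., death, suicide attempt, inpatient hospitalization) will be reported by telephone within 2 business days to the IRB of MGH".

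On the use of the data, Section VII.a states: "This DSMB will monitor safety issues, including the review of adverse events".

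Two other routes collect safety information in all arms. For the Cardiac Events (CE) survey, Section VI, Protection Against Risks, states: "The survey will ask patients whether they have been hospitalized for any of a variety of cardiac conditions". The same section has the PHQ-9 and ASRM monitor mood, with automated messages and an alert to the principal investigator at set scores. Neither route is described as limited to study-related problems. The wording of the two AEQ items is not reproduced anywhere.

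**The concern.** Relatedness is normally judged after an event has been captured, by someone who can see the whole picture. Under the Section IV.c description the participant makes that judgement first, and an event the participant thinks unrelated is never reported. Study clinicians then cannot assess it, and the promised summary of all adverse events cannot be complete.

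This matters more in a trial run online, where self-report is the main source of safety information. Participants also know whether they receive a therapy program, so willingness to call an event study-related could differ between the therapy arms and the Fitbit-only arm. If it did, recorded rates could differ with no true difference, or a true difference could be hidden.

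There is a second, smaller problem. Both descriptions of the survey look back to the start of participation, and the survey is given five times, so one event can be reported more than once.

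**Working it through.** **1. The sections side by side.** Section IV.c restricts the AEQ to study-related events. The Section IV Overview does not, and Section VII.b needs all events. A survey built to Section IV.c cannot by itself supply what Section VII.b promises. One built to the Overview can.

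**2. Which events depend on the AEQ.**

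- Cardiac hospitalization: covered by the CE survey, with no filter on cause.
- Depressive and manic symptoms and suicidal ideation: covered by the PHQ-9 and ASRM, with no filter on cause.
- Suicide attempt and non-cardiac hospitalization: the PHQ-9 and ASRM measure symptoms and ideation, and the CE survey concerns cardiac conditions. No other survey is described as asking about these.
- Physical injury: Section VI, Potential Risks to Subjects, directs injured participants to outside care and does not ask them to tell the study.

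For the last two groups the AEQ is the only systematic route described.

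**3. Illustration of size.** The documents state no adverse event rate, attribution rate or safety comparison, so there is no figure of theirs to reproduce. Inputs from Section III: 200 CBT + 200 MBCT = 400 therapy participants, and 100 Fitbit-only. Assumptions: a true event rate p = 10% in both groups, at most one event per participant, and probabilities a_T (therapy) and a_C (control) that a participant calls the event study-related.

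- True events: 400 × 0.10 + 100 × 0.10 = 40 + 10 = 50.
- Recorded events: 40 × a_T and 10 × a_C.
- Recorded rate ratio: (p × a_T)/(p × a_C) = a_T/a_C, whatever p is.
- Fraction missed: 1 − (0.8 × a_T + 0.2 × a_C), also free of p.

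| a_T | a_C | Therapy recorded | Control recorded | Ratio | Missed of 50 |
|---|---|---|---|---|---|
| 1 | 1 | 40/400 | 10/100 | 1.0 | 0 |
| 0.5 | 0.5 | 20/400 | 5/100 | 1.0 | 25 |
| 0.8 | 0.4 | 32/400 | 4/100 | 2.0 | 14 |
| 0.5 | 0.25 | 20/400 | 2.5/100 | 2.0 | 27.5 |
| 0.5 | 0.2 | 20/400 | 2/100 | 2.5 | 28 |
| 0.6 | 0.2 | 24/400 | 2/100 | 3.0 | 24 |
| 0.2 | 0.5 | 8/400 | 5/100 | 0.4 | 37 |

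These are expected counts. Equal attribution loses events but leaves the ratio at 1. Unequal attribution distorts the ratio in either direction; for example, 50% versus 20% gives 5% versus 2% with no true difference. The first row is the result when all events are asked about.

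**4. Look-back.** With surveys at weeks 2, 4, 6, 8 and 16, all starting from study entry, an event before week 2 falls inside all five windows. An event between weeks 2 and 4 falls inside four, between 4 and 6 three, between 6 and 8 two, and after week 8 one. No rule for removing repeats is stated.

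**The case against.** The strongest reply is that Section IV.c is a one-line description and the items themselves are not shown. They might ask first about any event and then about its relation to the study, as the Overview suggests. That stands: the documents disagree with each other, but they do not show that the survey in use has the filter. A reader might infer that the survey does make participants judge causality and does undercount, and the documents do not support stating that as fact.

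A reader might also infer that the AEQ is the only way to learn of non-cardiac problems. It is not. The PHQ-9 and ASRM are given to every arm at weeks 1, 2, 4, 6, 8 and 16 and monitor the main psychiatric risk. The CE survey is also introduced more broadly, as covering possible cardiovascular symptoms. What these routes leave open is narrower: injury, non-cardiac hospitalization and suicide attempt.

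A further tempting reading is that the safety comparison between arms seen by the DSMB is biased. Section VII.a has the DSMB review adverse events but mentions no tabulation by arm, and Section VIII contains no adverse event analysis. Nor is unequal attribution shown. Controls wear a study Fitbit for 16 weeks and complete the same assessments, so they too have something to attribute an event to. Bias by arm is a possibility only.

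Finally, repeated reports need not become repeated counts, because data are coded to participants and could be reconciled. That is true, but the plan does not say that it will be done.

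**Conclusion.** The conflict between Section IV.c on one side and the Section IV Overview and Section VII.b on the other is plain in the text and should be resolved. If the survey follows Section IV.c, events outside the cardiac and mood instruments may be lost before a clinician sees them, and the loss may be uneven between arms. Both consequences are conditional on wording that the documents do not show.

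The size is unknown. Over the assumed attribution rates below 1, between 14 and 37 of 50 events are missed and the recorded ratio runs from 0.4 to 3.0 when the true ratio is 1. These ranges reflect the assumptions and are not estimates for this trial. They also apply only to events that depend on the AEQ, not to all safety events. The repeat-reporting problem is certain in the described look-back, but it affects counts only if repeats are not reconciled.

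**What to change.** Reconcile the AEQ entry in Section IV.c, the Overview of Section IV and Section VII.b, and reproduce the two items in the protocol. The survey should ask every arm about any adverse event, whatever the participant thinks caused it. Study clinicians should judge relatedness afterwards, masked to arm where possible.

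Change the look-back in both Section IV.c and the Overview to the period since the last completed survey. Aligning Section IV.c with the Overview alone would remove the filter on cause but not the repeated look-back, because the Overview also counts from the start of the study.

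The cost is rewording two online questions and the matching protocol text. The downside is more unrelated minor events for clinicians to review.
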